4.1.2 Summarization by Visit

Data summarized by study visit will be based on the nominal, scheduled visit label as reported on the eCRF for each treatment group. Each treatment period consists of 42 days and study visits in Treatment Period 2 will be labeled according to the respective day within that treatment period. For example, the Day 63 visit occurs during Treatment Period 2 and will be labeled as Day 14 within that period. Data collected for the last subject treatment visit completed within each treatment period will be summarized separately for:

- The scheduled visit for those subjects who complete the scheduled end of treatment visit in each treatment period per protocol. This will be the scheduled Day 42 for subjects in Treatment Period 1 and Day 91 for subjects in Treatment Period 2. This summary will be labeled as "Day 42" in the analysis; and
- The last treatment visit completed on-study, combining data collected for subjects who complete the scheduled end of treatment visit, as well as the visit data for those subjects who discontinue the study early. This summary will be labeled as "Day 42/ET" in the analysis.

Data collected at unscheduled visits within the double-blind treatment period will not be included in by-visit summaries, but will be considered when endpoint derivations potentially include multiple visits (e.g., determination of baseline value, determination of worst post-baseline value, etc.). All data will be included in subject listings.

Any summarization of data collected during the follow-up period will be presented separately and will be based on the nominal, scheduled visit label as reported on the eCRF.

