4.5 Safety Evaluation

Safety analysis will be carried out for the SAF, to include all subjects who receive at least one capsule of IP. Subjects who do not complete both treatment periods, for whatever reason, will have all available data up until the time of termination included in the analysis. For safety analysis presented by study visit, unless otherwise stated, the

Confidential Page 23 of 28

baseline value will be the last measurement reported prior to the first dose of any IP at Day 1 during Treatment Period 1 or Day 50 during Treatment Period 2.

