4.5.2 Adverse Events

Treatment-emergent AEs are defined as those AEs with onset after the first dose of IP or existing events that worsened after the first dose during the study.

Treatment-emergent AEs will be summarized by treatment group through the end of Treatment Period 2. Select TEAE summaries through the end of Treatment Period 2 will also be presented by treatment period. Any AEs reported during the post treatment Follow-up period will be summarized separately by treatment sequence.

Each TEAE will be assigned to a single treatment using the date and time of onset. A TEAE that occurs after the first dose of IP in Treatment Period 1 but before the first dose of the IP in Treatment Period 2 will be assigned to the treatment associated with Treatment Period 1. This includes TEAEs that may occur in the washout interval between treatment periods.

A TEAE that continues over both treatment periods will be counted only once in the period during which the event started unless the TEAE worsens in severity, in which case the TEAE will be attributed to the treatment period during which it progressed to its most severe intensity. Events reported with a partial onset date (e.g., month and year are reported but the day is missing) will be considered to be treatment-emergent if it cannot be confirmed that the event onset was prior to the first dose of IP based on the available date entries.

Verbatim terms on case report forms will be mapped to preferred terms and system organ classes using the Medical Dictionary for Regulatory Activities (MedDRA, version 24.1).

Summaries that are displayed by system organ class and preferred terms will be ordered by descending incidence of system organ class and preferred term within each system organ class. Summaries displayed by preferred term only will be ordered by descending incidence of preferred term. Summaries of the following types will be presented:

- Overall summary of number of unique TEAEs and treatment-emergent serious adverse events (SAEs) and subject incidence of TEAEs meeting various criteria;
- Subject incidence of TEAEs by MedDRA system organ class and preferred term;
- Subject incidence of the most frequently-occurring TEAEs (i.e., TEAEs occurring in ≥ 10% of the SAF) by MedDRA preferred term;

Confidential Page 24 of 28

- Subject incidence of TEAEs by CTCAE grade, MedDRA system organ class, and preferred term;

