4.5.4 Clinical Laboratory Evaluation

All descriptive summaries of laboratory results will be based on data analyzed by the central laboratory and presented in Système International (SI) units, as suggested by the Center for Biologics Evaluation and Research and the Center for Drug Evaluation and Research *Position on Use of SI Units for Lab Tests* (Oct 2013). Summaries will also be presented in conventional units. All data will be included in by-subject data listings. Laboratory measurements identified as abnormal (i.e., outside the normal range) will also be listed separately by subject, laboratory test, and unit. In addition, normal ranges provided by the central laboratory will be presented in a separate listing.

Confidential Page 25 of 28

Clinical laboratory measurements, including serum chemistry and hematology, will be summarized by treatment group. Descriptive statistics will be presented for observed values and changes from baseline at each visit where parameters were scheduled to be collected per the clinical study protocol.

Where applicable, laboratory results will be classified as "low," "normal," or "high" with respect to the parameter-specific reference ranges (i.e., below the lower limit of the normal range, within the normal range, or above the upper limit of the normal range). Three-by-three contingency tables will be presented for each laboratory parameter to summarize the shift from the baseline category to the worst post-baseline measurement, defined as the value numerically farthest outside of the normal range across all post-baseline visits through the end of the study.

Summary results will include the count and percentage of subjects within each shift category and treatment group.

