4.5.5 Vital Signs, Physical Findings, and Other Observations Related to Safety

4.5.5.1 Vital Signs

Vital sign parameter measurements will be summarized by treatment group. Descriptive statistics will be presented for results and change from baseline at each visit where parameters were scheduled to be collected.

4.5.5.2 12-Lead Electrocardiogram

Select twelve-Lead ECG interval parameters to include heart rate, PR interval, QRS duration, and corrected QT (QTc) interval will be summarized by treatment group. Summaries of ECGs performed in triplicate will be based on the mean of the triplicate measurements at each time point. For visits where the interpretation is provided in triplicate, the worst interpretation will be used for analysis. Descriptive statistics will be presented for observed values and changes from baseline at each visit where parameters were scheduled to be collected.

Twelve-lead ECGs will be classified by the investigator as "normal," "abnormal, not clinically significant," or "abnormal, clinically significant." Three-by-three contingency tables will be presented to summarize the shift from the baseline category to the worst post-baseline value. Summary results will include the count and percentage of subjects within each shift category and treatment group.

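### The lab shift table is reported by treatment group, but its worst value is not confined to the period in which that treatment was taken

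*SAP*

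**What the plan says.** - **SAP 4.5.4** plans three-by-three tables (low, normal, high) that set each subject's starting category against one worst later value. That value is "defined as the value numerically farthest outside of the normal range across all post-baseline visits through the end of the study". On how the tables are laid out, the section adds: "Summary results will include the count and percentage of subjects within each shift category and treatment group".
- **SAP 4.1.2** qualifies this in two ways. "Any summarization of data collected during the follow-up period will be presented separately". Unscheduled values stay out of by-visit summaries but do count in derivations such as "determination of worst post-baseline value".
- **SAP 4.5** sets a baseline that restarts before Day 50, but introduces it with "For safety analysis presented by study visit, unless otherwise stated". A worst-value shift table is not an analysis by visit.
- **SAP 4.5.2** handles the crossover explicitly for adverse events: "Each TEAE will be assigned to a single treatment using the date and time of onset". For the end of the study: "Any AEs reported during the post treatment Follow-up period will be summarized separately by treatment sequence". Laboratory values have no counterpart to either rule.
- **SAP 4.5.5.2** plans a similar ECG table to "summarize the shift from the baseline category to the worst post-baseline value", by treatment group, with no window stated.
- **Protocol 12.1.5 and SAP 3.4.2.2** schedule laboratory samples at Screening, Day 0, Day 42, Day 91 or early termination, and the End of Trial visit (Day 119). Nothing is scheduled between Day 42 and the first Period 2 dose.

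**The concern.** A table headed by treatment should show values taken on that treatment. Here the definition runs to the end of the study, and in a crossover that takes in the other treatment. In the placebo-first sequence, an NB-001 abnormality at Day 91 can become the worst value in the placebo row. In the NB-001-first sequence, a placebo abnormality at Day 91 can enter the NB-001 row.

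The primary objective is safety, the primary endpoint includes clinically significant laboratory changes during NB-001 treatment (Protocol 5.2.1), and placebo is the only comparator. A table that mixes the two periods pulls the rows together and understates any difference.

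**Working it through.** The plan gives no figure that depends on this definition, so there is none to reproduce. The visit mapping comes from the documents. The abnormality rates are assumptions, because the documents give none.

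**Step 1: scheduled values feeding each row.** A/P is NB-001 then placebo; P/A is the reverse.

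| Row | Sequence | Within-period window | As written, period baseline | As written, one pre-Day 1 baseline |
|---|---|---|---|---|
| NB-001 | A/P | Day 42 | Days 42, 91, 119 | Days 42, 91, 119 |
| NB-001 | P/A | Day 91 | Days 91, 119 | Days 42, 91, 119 |
| Placebo | P/A | Day 42 | Days 42, 91, 119 | Days 42, 91, 119 |
| Placebo | A/P | Day 91 | Days 91, 119 | Days 42, 91, 119 |

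Applying SAP 4.1.2 removes Day 119 from every cell. Day 91 stays in the Period 1 rows.

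**Step 2: formulas without Day 119, period baselines.** Let q be the chance of an abnormal value at a visit on NB-001 and b the chance on placebo. Let U be the chance of an abnormal value at Day 42 or Day 91. Assume Day 0 is normal, sequences are equal, data are complete, and there is no period or carry-over effect, so U is the same in both sequences.

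- NB-001 row: (U + q)/2
- Placebo row: (b + U)/2
- Difference: (q − b)/2, because U cancels whatever the within-subject correlation
- With a within-period window: q − b

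**Step 3: marginal rates of an abnormal worst value, q = 20%, b = 5%.**

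- Independent visits: U = 1 − 0.80 × 0.95 = 0.24. NB-001 (0.24 + 0.20)/2 = 22.0%; placebo (0.05 + 0.24)/2 = 14.5%; difference 7.5 points.
- Full overlap (anyone abnormal on placebo is also abnormal on NB-001): U = 0.20. NB-001 20%; placebo (0.05 + 0.20)/2 = 12.5%; difference 7.5 points.
- Within-period window: 20% v 5%, difference 15 points.

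**Step 4: normal-to-abnormal shifts, which the table actually reports.** The Period 2 baseline is normally the Day 42 value, taken on the Period 1 treatment, so some subjects start Period 2 abnormal. For independent visits:

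- Period 2 on NB-001: 0.95 × 0.20 = 0.19. Period 2 on placebo: 0.80 × 0.05 = 0.04.
- Within-period window: NB-001 (0.20 + 0.19)/2 = 19.5%; placebo (0.05 + 0.04)/2 = 4.5%; difference 15 points.
- As written: NB-001 (0.24 + 0.19)/2 = 21.5%; placebo (0.24 + 0.04)/2 = 14.0%; difference 7.5 points.

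**Step 5: Day 119 included, marginal rates, independent visits, off-drug rate b at follow-up.** The three-visit union is 1 − 0.80 × 0.95² = 0.278.

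- NB-001: (0.278 + 0.24)/2 = 25.9%
- Placebo: (0.278 + 0.0975)/2 = 18.8%, where 0.0975 = 1 − 0.95²
- Difference: 7.1 points, equal to (1 − b)(q − b)/2

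Day 119 is not required for subjects entering the extension (Protocol 8.5), so a mixed data set lies between this case and Step 3.

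**Step 6: one pre-Day 1 baseline for both rows.** Both rows use the same visits, so both are 24.0% (27.8% with Day 119) and the difference is 0.

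**Range (marginal, independent visits, no Day 119, period baselines).**

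| q, b | As written | Difference as written | Difference within period |
|---|---|---|---|
| 20%, 0% | 20% v 10% | 10 points | 20 points |
| 20%, 10% | 24% v 19% | 5 points | 10 points |
| 10%, 5% | 12.3% v 9.8% | 2.5 points | 5 points |
| 30%, 5% | 31.8% v 19.3% | 12.5 points | 25 points |

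**The case against.** The best defence is that the SAP as a whole points to a within-period table. SAP 4.2 analyses the safety set by treatment received. SAP 4.1.2 organises visits by treatment group and relabels Period 2 visits by day within the period. SAP 4.5 restarts the baseline before Day 50. A programmer could reasonably infer a period window.

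That reading is plausible, but the text does not state it. The treatment-received clause says which treatment a subject is counted under and sets no window. Relabelling concerns by-visit summaries. The baseline rule is limited to by-visit analyses and sets no end to the post-baseline interval. Moreover, each period has only one scheduled post-baseline sample, so a worst value over several visits would have only unscheduled samples to add. The wording fits a span over both periods better.

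Three parts of the objection stand:

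- Halving is not simply what the text produces. It needs the Day 50 baseline to be borrowed from SAP 4.5. The possible results are no distortion (within-period reading), about half, or no contrast at all.
- The 22.0% and 14.5% are marginal rates, not shifts; Step 4 gives the shifts.
- The table is descriptive and untested.

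A reader might go further and infer that the plan would hide a laboratory signal, or that the primary safety conclusion is compromised. The documents do not support that. Clinical significance is judged by the Investigator. Observed values and changes are summarised by visit and treatment, abnormal values are listed by subject, and adverse events go to one treatment by onset. A reader might also infer that the ECG table has the same wrong rule; it only leaves its window unstated.

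**Conclusion.** The concern holds as a defect in one stated rule. SAP 4.5.4 combines a whole-study window with reporting by treatment, and no section restores the period limit. The follow-up rule in SAP 4.1.2 removes at most Day 119.

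Read literally with period baselines, the NB-001 minus placebo difference falls to about half. With a single pre-Day 1 baseline it vanishes. The half result rests on equal sequences, complete data, normal Day 0 values and no period or carry-over effect. Without Day 119 it does not depend on the within-subject correlation. The percentages rest on assumed rates. The damage is confined to a descriptive safety table whose main safeguards lie elsewhere in the plan, but the correction is nearly free and should be made before the SAP is final.

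**What to change.** In SAP 4.5.4:

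- Limit the worst post-baseline value for each treatment, from scheduled or unscheduled samples, to values after the first dose of that period and before the first dose of the next. For Period 2, and for subjects who leave early, end the window at the Day 91/early termination visit.
- State that the shift-table baseline is the period baseline. A footnote should say that for Period 2 this is normally the Day 42 value on the previous treatment.
- Present Day 119 and other follow-up values separately, as SAP 4.1.2 already requires. Showing them by sequence would match the handling of adverse events.

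In SAP 4.5.5.2, state the same window for the ECG shift table.

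The cost is a few sentences, with no new data or procedures. There are two side effects. Abnormalities first seen at follow-up leave the shift table and appear only in the follow-up display and listings. An unscheduled wash-out value can count both as Period 1 post-baseline and as the Period 2 baseline.

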4.5.5 Vital Signs, Physical Findings, and Other Observations Related to Safety

4.5.5.1 Vital Signs

Vital sign parameter measurements will be summarized by treatment group. Descriptive statistics will be presented for results and change from baseline at each visit where parameters were scheduled to be collected.

4.5.5.2 12-Lead Electrocardiogram

Select twelve-Lead ECG interval parameters to include heart rate, PR interval, QRS duration, and corrected QT (QTc) interval will be summarized by treatment group. Summaries of ECGs performed in triplicate will be based on the mean of the triplicate measurements at each time point. For visits where the interpretation is provided in triplicate, the worst interpretation will be used for analysis. Descriptive statistics will be presented for observed values and changes from baseline at each visit where parameters were scheduled to be collected.

Twelve-lead ECGs will be classified by the investigator as "normal," "abnormal, not clinically significant," or "abnormal, clinically significant." Three-by-three contingency tables will be presented to summarize the shift from the baseline category to the worst post-baseline value. Summary results will include the count and percentage of subjects within each shift category and treatment group.

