5.2. Endpoints

5.2.1. Primary Endpoint

• Type, frequency, severity, and causality of TEAEs, treatment-emergent serious adverse events (TESAEs), clinically significant changes from baseline in: laboratory tests, electrocardiograms (ECGs), vital signs, and physical examination findings during treatment with NB-001

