15.2. General Procedures

Trial population and baseline data collection (e.g., subject disposition and demographics) will be presented by treatment sequence and for all subjects combined. Efficacy and safety endpoints will be summarized by treatment group.

Continuous variables will be summarized with descriptive statistics (number evaluated, mean, standard deviation, median, minimum, and maximum). Categorical variables will be presented as counts and percentages within each category. As appropriate, 95% confidence intervals will be included.

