15.5. Safety Analyses

AEs will be mapped to preferred terms and system organ class using the Medical Dictionary for Regulatory activities (MedDRA). TEAEs will be mapped to IP by comparing the event onset to the date of first dose of IP within each treatment period. Incidence rates for TEAEs will be

summarized by system organ class and preferred term by treatment group. In addition, TEAEs will be summarized by severity and relationship to IP by treatment group. Subjects will be counted once at each level of summation (i.e., overall, by system organ class, and by preferred term). Summaries by relationship to IP will count a subject once at each level of summation based on the closest relationship; summaries by severity will count a subject once at each level of summation using the highest severity reported. As this is a crossover trial in which subjects are randomized to one of two treatment sequences: NB-001 followed by placebo (treatment sequence A/P) or placebo followed by NB-001 (treatment sequence P/A), all subjects who receive at least one dose of IP (NB-001 or placebo) in treatment period will be included in summaries of TEAE data for both NB-001 and placebo, according to the treatment being taken at the time of TEAE onset. A detailed description of the planned TEAE analyses will be presented in the SAP.

All other safety parameters including clinical laboratory values, vital sign measurements, and ECG interval results will be summarized using descriptive statistics for continuous variables and counts and percentages for categorical variables by treatment group. Results will be presented for the observed value and the change from baseline by time point.

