4.7 Changes in the Conduct of the Study or Planned Analyses

The protocol defined the ENR as all subjects who meet all eligibility criteria and receive at least 1 complete daily dose (400 mg) of IP. This definition was restricted in the SAP to remove the "at least 1 complete daily dose" requirement. All subjects who meet eligibility criteria and consent to study participation will be include in this analysis set.

Section 15.4 of the protocol states that response rates will be compared between treatment groups using Fisher's exact test. This test is not appropriate for this cross-over study design, and the McNemar's test will be used instead.

Confidential Page 27 of 28

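### Labs, ECG intervals and vital signs get by-treatment descriptive columns but no interval for the within-child NB-001 minus placebo difference, and the change-from-baseline columns do not fill the gap

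*SAP*

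**What the plan says.** Protocol 5.2.1 places these data in the primary endpoint next to treatment-emergent adverse events, as "clinically significant changes from baseline in: laboratory tests, electrocardiograms (ECGs), vital signs, and physical examination findings during treatment with NB-001".

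The planned analysis is descriptive throughout. Protocol 15.5 says that safety parameters other than adverse events "will be summarized using descriptive statistics for continuous variables and counts and percentages for categorical variables by treatment group". The SAP follows:

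- 4.5.5.1: "Vital sign parameter measurements will be summarized by treatment group".
- 4.5.5.2: "Select twelve-Lead ECG interval parameters to include heart rate, PR interval, QRS duration, and corrected QT (QTc) interval will be summarized by treatment group".
- 4.5.4: "Clinical laboratory measurements, including serum chemistry and hematology, will be summarized by treatment group".

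Each section covers observed values and change from baseline by visit. Labs and ECG also get baseline-to-worst shift tables, and abnormal laboratory values are listed separately. SAP 4.1.1 limits the routine statistics for continuous variables to counts, mean, SD, median, quartiles and extremes. Protocol 15.2 adds "As appropriate, 95% confidence intervals will be included", but neither document names a safety contrast to which that would apply.

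SAP 4.5 takes the safety baseline as the last value before the first dose on Day 1 for Period 1, or on Day 50 for Period 2.

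**The concern.** Most children appear in both columns. The SD in each column describes the spread between children aged 6 to 17. It does not describe the uncertainty of the drug effect, which depends on how far the same child differs between the two periods. A reader given two means and two SDs cannot recover that uncertainty.

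Two things compound this. Children who leave during Period 1 contribute to one column only, so the columns hold partly different children. Nor does the plan adjust for period, which matters once the sequences are unequal in size.

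At stake is how precisely the report can describe a shift in, say, heart rate, QTc or creatinine. The efficacy model in SAP 4.4.4 uses the pairing through a subject effect and a period term. The continuous parameters of the primary safety endpoint do not get the same benefit.

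**Working it through.** The plan states no interval width or precision target for any safety parameter, so there is no figure of its own to reproduce. The sample-size statement concerns CGI-I only.

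**Inputs**

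- n = 30 children with both on-treatment values, taken from the evaluable number in SAP 4.6 (15 per sequence).
- Equal SD under both treatments. Results are in units of that SD.
- r, the within-child correlation between the two periods. This is assumed and shown over a range, because the documents give no value.

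**Step 1: interval width for NB-001 minus placebo on observed values**

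Columns read as independent groups: t(58) × √(2/30) = 2.002 × 0.258 = 0.517 SD.

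Within child, adjusted for period: t(28) × √(2(1 − r)/30), with t(28) = 2.048.

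| Assumed r | √(2(1 − r)/30) | Within-child half-width (SD) | Ratio to 0.517 |
|---|---|---|---|
| 0 | 0.258 | 0.529 | 1.02 |
| 0.25 | 0.224 | 0.458 | 0.89 |
| 0.5 | 0.183 | 0.374 | 0.72 |
| 0.7 | 0.141 | 0.290 | 0.56 |
| 0.8 | 0.115 | 0.237 | 0.46 |

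At r = 0 pairing gains nothing and costs a few degrees of freedom. To match the within-child standard error, unpaired columns would need 30/(1 − r) children each: 60 at r = 0.5 and 150 at r = 0.8.

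**Step 2: whether the change-from-baseline columns already do the job**

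Laboratory samples and ECGs are scheduled at Screening, Day 0, Day 42, Day 91 and Day 119 (SAP 3.4.2.2 and 3.4.2.5), with none at Day 49 or 50. Protocol Table 3 schedules no vital signs at Day 49, and its footnote makes those at Day 50 conditional on clinical need. Under the SAP 4.5 rule, the last value before the Day 50 dose will therefore usually be Day 42, the end of treatment in Period 1.

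Let τ be the true effect, with no carryover and no period effect:

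- NB-001 first: the NB-001 change (Day 42 − Day 0) averages +τ, and the placebo change (Day 91 − Day 42) averages −τ.
- Placebo first: the placebo change averages 0, and the NB-001 change averages +τ.
- With equal sequences, the NB-001 column averages τ and the placebo column (−τ + 0)/2 = −τ/2. The apparent difference is τ − (−τ/2) = 1.5τ.

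The variance is worse too. With within-child error variance σ² at each visit, the observed-value difference has variance 2σ². The difference of the two changes is ±(2 × Day 42 − Day 0 − Day 91), with variance (4 + 1 + 1)σ² = 6σ². The standard error is √3 ≈ 1.7 times as large. A 5,000-replicate simulation agreed: mean contrast 1.50 for a true effect of 1, with standard error 0.315 against 0.184 at r = 0.5.

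So the difference between change columns overstates a true effect and is noisier than the direct comparison of Day 42 with Day 91, which needs no Period 2 baseline.

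**The case against.** The strongest reply is that descriptive safety tables are conventional and are what Protocol 15.5 asks for. The endpoint leads with adverse events and, for these parameters, asks about clinically significant changes. That question concerns individual children and is served by shift tables, abnormal-value listings and adverse-event tables. All of this stands. It rules out the reading that these parameters alone carry the primary objective, or that side-by-side columns are all the plan provides.

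A reader might also infer that the plan applies an invalid independent-groups analysis. It does not: no such interval or test is planned, and the 0.52 SD half-width is only what a reader would get by treating the columns that way. Nor is the point estimate lost. If every child has both values, the difference in column means equals the mean within-child difference, and period effects cancel with equal sequences. What is missing is the uncertainty, the adjustment when sequences are unequal, and a common set of children when some leave early. The protocol synopsis assumes 10% dropout.

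SAP 4.7 rejects Fisher's exact test for response rates because "This test is not appropriate for this cross-over study design, and the McNemar's test will be used instead". That shows the authors considered pairing, but it concerns a hypothesis test, and none is planned here. It does not make the safety section internally inconsistent.

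Finally, change from baseline is itself a within-child quantity, and against change columns with a genuine pre-treatment baseline in each period the direct contrast would be only 0.72 times as wide. That baseline is not scheduled for labs or ECG in Period 2, and for vital signs it is only conditional, so this part of the reply does not succeed.

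**Conclusion.** The gap is real and moderate. For continuous labs, ECG intervals and vital signs, the plan specifies no uncertainty for the within-child treatment difference and no period adjustment, and its change-from-baseline columns are a poor substitute. The size depends on the unknown correlation: the half-width falls from 0.52 SD to 0.46 SD at r = 0.25 and to 0.24 SD at r = 0.8, with no gain at r = 0. This assumes 30 complete pairs and equal SDs. The 1.5-fold inflation of the change contrast assumes that Day 42 serves as the Period 2 baseline, equal sequences, and no carryover or period effect.

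The documents do not support calling this a breach of the protocol or a failure to address the primary endpoint. It is an inexpensive improvement that the sponsor should make.

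**What to change.** In SAP 4.5.4, 4.5.5.1 and 4.5.5.2, name a short fixed list: heart rate, systolic and diastolic pressure, PR, QRS, QTc, ALT, AST and creatinine. For each, report NB-001 minus placebo from the observed Day 42 and Day 91 values, with a 95% confidence interval from a model with treatment, period and subject, in children with both values. Label the intervals descriptive and report no p-values. Keep the existing SAF columns, shift tables and listings so that early leavers remain visible.

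The cost is a few lines of SAP text and an extra column in three table shells. Day 42 and Day 91 measurements are already scheduled, so no new data are needed. The drawbacks should be stated with the tables: nine intervals without multiplicity adjustment, restricted to children who reached both assessments, and ECG intervals from recordings that Protocol 12.1.4 does not time relative to dosing.
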